7.2.4.1 Health-related Quality-of-Life Assessments

Daily Ulcerative Colitis Scale for Children and Caregivers

Shire has developed an electronic daily sign and symptom diary, the DUCS. Two versions have been developed: 1 patient-reported outcome (PRO) to be self-completed by children aged 8-17 years and 1 observer-reported outcome (ObsRO) to be completed by caregivers of children aged 5-10 years. Both the PRO and ObsRO will be completed by children aged 8-10 years; however, the ObsRO will be used for the secondary endpoint analysis. The data obtained from the PRO in this age group will provide information for future use to determine if children/adolescents can reliably complete the PRO.

The concept elicitation phase has informed the content of the diaries and provided for development of a draft item pool and draft measures. Cognitive debriefing interviews have been completed on these draft measures. This phase involved conducting interviews with UC patients and caregivers to evaluate the clarity, understanding, relevance, and comprehension of the draft PRO and ObsRO daily diaries as well as usability of the electronic device and feasibility of daily use at home.

Overall Current Health

An Overall Current Health item will be included in the e-diary. The Overall Current Health item has been tested in cognitive debriefing interviews with the DUCS.

PUCAI

The PUCAI is a physician-administered measure that focuses on 6 key signs and symptoms of UC and activity limitations (Turner et al. 2007). The PUCAI yields a total score ranging from 0-85 with higher scores being worse. Recommended cut-off scores to differentiate disease activity are <10 (remission); 11-30 (mild); 31-64 (moderate) and >65 (severe) (Turner et al. 2009). Evaluation of the construct validity of the PUCAI revealed that it was highly correlated with physician's global assessment of disease activity and PUCAI scores were highly predictive of the need for escalating medical therapy (Turner et al. 2009). See [Appendix 4](#).

Only sites who have executed a sublicense with Shire for PUCAI use will be able to collect PUCAI data for the study.

IMPACT III

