Summary of Change(s) Since Last Version of Approved Protocol		
Amendment Number	Amendment Date	Global/Country/Site Specific
2	14 Jul 2014	Global
Description of Change		Section(s) Affected by Change
Updated United States Premier Research Medical Monitor.		Emergency Contact Information
Data Monitoring Committee added.		Abbreviations, Section 9.5
Corrected definition of Clinical Response by removing “Week 8”.		Definitions
“Continuity-corrected” chi-squared test was added to the method to test the primary/secondary endpoints.		Synopsis, Section 9.8.3.1
Revised number of active study sites from 35 to 43		Synopsis, Section 3.3
Added comment to footnotes to clarify that final visit of Double-blind Acute Phase and of the Open-label Acute Phase will be used as Week 0 for the subject’s next phase of participation.		Table 1, Table 2
Clarified footnote regarding endoscopy requirements for subjects entering the Double-blind Maintenance Phase directly.		Table 3
Added height assessments.		Table 1, Table 2, Table 3
Text amended to allow for data from an endoscopy performed within 7 days prior to the Screening Visit (Visit 1) to be used in place of an endoscopy performed during the Screening Visit (Visit 1) or Baseline Visit (Visit 2) for subjects entering the Double-blind Acute Phase.		Table 1, Table 3, Section 7.1.1.1, Section 7.1.1.2, Section 7.2.1.2
Removed height from physical examination.		Section 7.2.2.2
Added IRT Entry to schedule of assessments.		Table 1, Table 2, Table 3
Added text to indicate that PUCAI will not be collected by all study sites.		Table 1, Table 2, Table 3, Section 7.1.1.2, Section 7.1.2.2, Section 7.1.3.2, Section 7.1.4.3, Section 7.2.3.1
Text related to description of subjects who may have an endoscopy removed for clarity.		Table 2
Added weight assessment to the end of the Double-blind Maintenance Phase.		Table 3, Section 7.2.2.3
Removed blank column for 90 days.		Table 5
Revised information to describe the rationale for the study design.		Section 2.1
Added clarification that an additional endoscopy is not required for subjects enrolling into the Double-blind Maintenance Phase from the Double-blind Acute Phase or the Open-label Acute Phase.		Synopsis, Section 3.1, Section 4.3
Corrected visit number.		Section 4.5
Information regarding the provision of additional care after the study included.		Section 7.1.6
Clarified entry requirements for Double-blind Maintenance Phase by adding endoscopy score component.		Section 3.1, Section 7.1.1.2

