4.3.4 Pediatric Ulcerative Colitis Activity Index

The PUCAI is a physician-administered measure that focuses on 6 key signs and symptoms of UC and activity limitations ([Turner et al., 2007](#)). The PUCAI yields a total score ranging from 0-85 with higher scores being worse. Recommended cut-off scores to differentiate disease activity are <10 (remission); 11-30 (mild); 31-64 (moderate) and >65 (severe) ([Turner et al., 2009](#)). Evaluation of the construct validity of the PUCAI revealed that it was highly correlated with physician's global assessment of disease activity and PUCAI scores were highly predictive of the need for escalating medical therapy ([Turner et al., 2009](#)).

Only sites who have executed a sub-license with Shire for PUCAI use will be able to collect PUCAI data for the study.

Item	Points
1. Abdominal pain	
No pain	0
Pain can be ignored	5
Pain cannot be ignored	10
2. Rectal bleeding	
None	0
Small amount only, in less than 50% of stools	10
Small amount with most stools	20
Large amount (>50% of the stool content)	30
3. Stool consistency of most stools	
Formed	0
Partially formed	5
Completely unformed	10
4. Number of stools per 24 hours	
0–2	0
3–5	5
6–8	10
>8	15
5. Nocturnal stools (any episode causing wakening)	
No	0
Yes	10
6. Activity level	
No limitation of activity	0
Occasional limitation of activity	5
Severe restricted activity	10
Sum of PUCAI (0–85)	

© Copyright to The Hospital for Sick Children,
Toronto, Canada, 2006.

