5.2.5 Double-blind Acute Phase Safety Analysis Set

The Double-blind Acute Phase Safety Analysis Set will consist of randomized subjects who have taken at least 1 dose of investigational product during the Double-blind Acute Phase.

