5.8.2 Secondary Efficacy Endpoints and Analysis

The secondary endpoints for this study are defined separately for both the Double-blind Acute and Double-blind Maintenance Phases and will be conducted using the appropriate Safety Analysis Set for the phase.

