5.8.2.1 Double-blind Acute Phase

- The proportion of subjects with a clinical and endoscopic response at Week 8, defined as UC-DAI ≤ 2 with rectal bleeding=0 and stool frequency ≤ 1 and PGA=0, and with mucosal healing (endoscopy score ≤ 1) based on central reading. In addition, there must be at least a 1-point reduction in endoscopy score from baseline. This endpoint will be compared between treatment arms using a continuity corrected chi-squared test. If any of the expected cell counts are very low (i.e., less than 5), then Fisher's Exact Test will be used as an alternative analysis method. Subjects with missing data at Week 8 will be assumed not to have had a clinical response. Subjects who completed week 8 but who did not have central reading endoscopies at both baseline and week 8 will be excluded.
- The proportion of subjects with a clinical and endoscopic response at Week 8, defined as UC-DAI ≤ 2 with rectal bleeding=0 and stool frequency ≤ 1 and PGA=0, and with mucosal healing (endoscopy score ≤ 1) based on local reading. In addition, there must be at least a 1-point reduction in endoscopy score from baseline. This endpoint will be compared between treatment arms using a continuity corrected chi-squared test. If any of the expected cell counts are very low (i.e., less than 5), then Fisher's Exact Test will be used as an alternative analysis method. Subjects with missing data at Week 8 will be assumed to be treatment failures. Subjects with missing data at Week 8 will be assumed not to have had a clinical response. Subjects who completed week 8 but who did not have local reading endoscopies at both baseline and week 8 will be excluded.
- The change in the DUCS score from baseline to Week 8 of the Double-blind Acute Phase. This endpoint will be compared between treatment arms using an analysis of covariance (ANCOVA), including treatment arm as a factor and the baseline DUCS score as a covariate in the model.
- The percentage of subjects with an improvement (change of ≥ 20 points) in PUCAI score from baseline to Week 8 of the Double-blind Acute Phase. This endpoint will be compared between treatment arms using a continuity corrected chi-squared test. If any of the expected cell counts are very low (i.e., less than 5), then Fisher's Exact Test will be used as an alternative analysis method. Subjects with missing data at Week 8 will be assumed not to have had a clinical response.

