5.8.2.2 Double-blind Maintenance Phase

- The proportion of subjects who have maintained a clinical and endoscopic response at Week 26, defined as UC-DAI ≤ 2 with rectal bleeding=0 and stool frequency ≤ 1 and PGA=0 and with mucosal healing (endoscopy score ≤ 1) based on central reading. This endpoint will be compared between treatment arms using a CMH test stratifying by Week 8 responder status. Subjects with missing data at Week 26 will be assumed not to have had a clinical response. If there are an insufficient number of subjects with central reading endoscopy data, then the CMH test will not be performed. The number and percentage of subjects with clinical and endoscopic response – based on central response will be presented by treatment arm.
- The proportion of subjects who have maintained a clinical and endoscopic response at Week 26, defined as UC-DAI ≤ 2 with rectal bleeding=0 and stool frequency ≤ 1 and PGA=0, and with mucosal healing (endoscopy score ≤ 1) based on local reading. This endpoint will be compared between treatment arms using a CMH test stratifying by Week 8 responder status. Subjects with missing data at Week 26 will be assumed not to have had a clinical response. If there are an insufficient number of subjects with central reading endoscopy data, then the CMH test will not be performed. The number and percentage of subjects with clinical and endoscopic response – based on local response will be presented by treatment arm.
- The change in the DUCS score from Double-blind Maintenance Phase Week 0 to Week 26. This endpoint will be compared between treatment arms using an analysis of covariance, including treatment arm as a factor, the DUCS score at Double-blind Maintenance Phase Week 0 and Week 8 responder status as covariates in the model.
- The percentage of subjects in remission (PUCAI < 10) at Double-blind Maintenance Phase Week 26. This endpoint will be compared between treatment arms using a CMH test stratifying by Week 8 responder status. Subjects with missing data at Week 26 will be assumed not to have had a clinical response.

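### Both PUCAI secondary endpoints count every dosed subject, including any at sites not licensed to collect PUCAI, who can then only be failures

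*SAP*

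**What the plan says.** - **Who can collect the score.** SAP 4.3.4: "Only sites who have executed a sub-license with Shire for PUCAI use will be able to collect PUCAI data for the study". Protocol 7.2.4.1 says the same: "Only sites who have executed a sublicense with Shire for PUCAI use will be able to collect PUCAI data for the study". The schedules of assessments mark the PUCAI as done only where applicable. As background, the Amendment 2 entry in Protocol Appendix 1 reads "Added text to indicate that PUCAI will not be collected by all study sites".
- **Denominator.** SAP 5.8.2 says the secondary endpoints "will be conducted using the appropriate Safety Analysis Set for the phase". For the acute phase, SAP 5.2.5 reads "The Double-blind Acute Phase Safety Analysis Set will consist of randomized subjects who have taken at least 1 dose of investigational product" in that phase. SAP 5.2.7 mirrors it for maintenance. Neither definition depends on the site's license. The titles of outputs 14.2.2.1.4 and 14.2.2.1.17 to 14.2.2.1.20 name these same sets.
- **Missing data.** The acute PUCAI bullet (SAP 5.8.2.1) says "Subjects with missing data at Week 8 will be assumed not to have had a clinical response". The maintenance PUCAI bullet (SAP 5.8.2.2) says "Subjects with missing data at Week 26 will be assumed not to have had a clinical response". Neither makes an exception for sites that could not collect the score.
- **Contrast.** In the same section, the central-reading endoscopy bullet does make an exception: "Subjects who completed week 8 but who did not have central reading endoscopies at both baseline and week 8 will be excluded". The local-reading bullet has the equivalent sentence.

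**The concern.** A score that a site was never permitted to collect is not a dropout or a missed visit. Counting it as non-response puts subjects in the denominator who cannot enter the numerator, whatever the treatment does. SAP 5.1 describes an estimation study, so the percentage per arm is the main product of these endpoints, and it would be too low whenever unlicensed sites have enrolled subjects who would have met the criterion.

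No planned analysis of these two endpoints removes the problem. The complete-case and last-observation-carried-forward analyses (SAP 7.2 and 7.7.1) cover the primary endpoint only, and SAP 6 lists no PUCAI provision.

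The rule is also loosely worded in two ways. It imputes clinical response, which SAP 8.2 defines by the partial UC-DAI and not by the PUCAI. And the acute endpoint is a change from baseline, yet the rule covers a missing Week 8 value only, not a missing baseline.

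**Working it through.** The plan states no PUCAI rate and no licensed-site share, so there is no figure of its own to reproduce. What follows is illustrative.

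**Inputs from the documents.** Acute sample size 53 (SAP 3.5), taken here as 26 low dose and 27 high dose. Maintenance at least 80 (SAP 3.5), taken as 40 per arm. Allocation 1:1, stratified by weight group and not by site or license status (SAP 3.3).

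**Assumptions.** True rates 50% (low) and 70% (high), the same at licensed and unlicensed sites; no other missing data; f is the share of an arm at unlicensed sites.

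**Formula.** Expected reported rate = true rate × (1 − f). The highest rate an arm can report is 1 − f.

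**1. Equal f in both arms**

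| f | Low | High | Difference (points) |
|---|---|---|---|
| 0 | 50.0% | 70.0% | 20.0 |
| 10% | 45.0% | 63.0% | 18.0 |
| 25% | 37.5% | 52.5% | 15.0 |
| 50% | 25.0% | 35.0% | 10.0 |

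**2. Unequal f, with 13 of the 53 acute subjects at unlicensed sites**

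- Split 4 low, 9 high: 0.50 × 22/26 = 42.3% and 0.70 × 18/27 = 46.7%, a difference of 4.4 points. The ceilings are 22/26 = 84.6% and 18/27 = 66.7%.
- Split 9 low, 4 high: 0.50 × 17/26 = 32.7% and 0.70 × 23/27 = 59.6%, a difference of 26.9 points.
- Chance of a split at least that uneven: hypergeometric (53 subjects, 13 unlicensed, 26 drawn to the low arm), P(low arm has 4 or fewer, or 9 or more) = 0.202.

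**3. On average and in a single trial.** The expected difference as written is 20 × (1 − 13/53) = 15.1 points. Simulation agrees: about 15 points as written against about 20 in licensed-site subjects. Even so, the difference as written is larger in absolute size than the licensed-site difference in about 30% of simulated trials. With 20 of 80 subjects unlicensed and the same true rates, the figures are 15 against 20 points and about 23%.

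**4. One subject.** A single unlicensed-site subject lowers an arm's percentage by at most 100/26 = 3.8 points in the acute phase or 100/40 = 2.5 points in maintenance, and only if that subject would have met the criterion.

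**The case against.** **The effect may be zero.** Nothing in the documents shows that an unlicensed site enrolled anyone, and the amendment log shows only what was expected at the time. This stands as a limit on size: every value of f above is assumed. It does not alter what the rule does to any such subject.

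**Where applicable could mean the score is not missing at unlicensed sites.** That phrase in the schedules marks where the score is collected. It takes nobody out of the Safety Analysis Set, so the subject stays in the denominator without a score.

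**The separate table specifications might restrict the denominator.** SAP 1.1 does refer to such a document, which is not available here. But the SAP text and its output titles both name the full set, and a rule that fixes an endpoint's denominator belongs in the SAP.

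**The data can be recovered elsewhere.** Partly true. The by-visit PUCAI summaries (SAP 5.8.3.2; outputs 14.2.2.2.6 and 14.2.2.2.22) include a category below 10, so a reader can find the observed Week 26 remission rate. They do not give the Week 8 improvement of 20 points or more, which would have to be rebuilt from listing 16.2.6.5. Neither corrects the secondary endpoint itself.

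**The consequence is limited.** This is fair. The endpoints are secondary, the p-values are descriptive, and the outputs specified in SAP 5.8.2 are a percentage per arm and a test. SAP 7.6.2 asks for a difference and interval by stratum, but for clinical response, a UC-DAI term.

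**Missing as failure is conservative.** That does not help when the aim is to estimate a rate, and it is not reliably so between arms when f differs.

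**Conclusion.** The concern holds. The restriction on collection, the full-set denominator and the failure rule together make any subject at an unlicensed site a certain failure on both PUCAI endpoints. The arm percentage is then understated in expectation by the factor (1 − f), assuming similar true rates at licensed and unlicensed sites. A between-arm difference shrinks toward zero on average, but chance imbalance can push it either way in one trial. The size is unknown because f is not given, and it is nil if all enrolling sites are licensed. The primary endpoints are unaffected. This should be fixed before unblinding. The wording faults (clinical response, missing baseline) need correcting whatever f is.

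**What to change.** State in SAP 5.8.2.1 and 5.8.2.2 that the analysis set for the PUCAI endpoints is subjects in the phase Safety Analysis Set whose site held a PUCAI sub-license when the subject was randomized into that phase. Within that set:

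- a missing Week 8 change (baseline or Week 8 score absent) counts as no PUCAI improvement;
- a missing Week 26 score counts as not in PUCAI remission.

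This replaces the clinical-response wording. Apply it to outputs 14.2.2.1.4 and 14.2.2.1.17 to 14.2.2.1.20 and to the PUCAI summaries under SAP 7.6.2. Report the number excluded by arm, and list the scores from sites licensed mid-phase.

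**Cost.** One SAP statement per endpoint, a site license-date flag, and new denominators and titles for five outputs. The sponsor is party to the sub-license, so the date should be obtainable; the documents do not say it is in the database. License status at randomization is fixed before allocation, so the restriction adds no post-randomization selection.

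**Downsides.** Valid Week 26 scores from sites licensed mid-phase are listed but not analysed, and denominators fall. As an illustration (SAP 5.8.2 specifies no interval for these endpoints), the 95% half-width for one arm at 50% is 1.96 × √(0.25/n):

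- Acute: 19.2 points with 26 subjects, 21.9 with 20, 27.2 with 13.
- Maintenance: 15.5 points with 40 subjects, 17.9 with 30, 21.9 with 20.
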